3. INVESTIGATIONAL PLAN

3.1. Study Design

Fifteen patients (approximately 80% children) with WAS/ XLT will be enrolled and undergo baseline screening including not only blood drawing but also history of illness in the past, while ten additional WAS and XLT otherwise ineligible or unwilling patients who will not undergo study treatment and ten control subjects will undergo a one-time blood draw. The pediatric control and non-treatment WAS/XLT subjects will be pediatric patients who are having their blood drawn for reasons not related to an acute illness and will provide a limited amount of additional blood. The pediatric control and non-treatment WAS/XLT subjects will have their blood drawn at Cornell after giving consent. They will not be asked for more than 5-10 ml of blood per year of age up to a maximum of 30 ml total in one draw. Blood drawn will be studied for stem cells and

megakaryocytopoiesis, Immature Platelet Fraction (IPF), and platelet function (see table). These subjects will have their blood drawn for another purpose e.g. pre-op clearance for surgery and therefore it will be a small amount of extra blood posing a minimal risk to the subject. Subsequently, treatment patients will start on 2 mg/kg of eltrombopag and be seen every two weeks in the first month, and monthly for the first year. Although Promacta is commercially available in 25 mg and 50 mg tablets, it is also available for clinical studies in 12.5 mg tablets which will be provided by Novartis for this study. In this study, the starting dose will be based upon weight; patients over 50 kg will start at 50 mg daily unless they are of East Asian origin in which case they will use 25 mg as their initial dose. The dose of eltrombopag will be titrated for each subject based on their platelet response (see table 1). Overall, in this study, doses between 12.5mg every other day and 75mg once daily are anticipated to be required to maintain platelet counts between 50 and 400Gi/L. However, as explained in the provided dosing guidelines, the dose of eltrombopag will be reduced whenever the platelet count exceeds 200Gi/L in order to prevent it from reaching 400Gi/L. The goal is to have a platelet count in a safe hemostatic range, albeit not necessarily a normal platelet count.

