4. SUBJECT SELECTION AND WITHDRAWAL CRITERIA

4.1. Number of Subjects:

25 WAS/XLT Patients (10 of whom will have a blood draw only) + 10 Normal Control Patients = 35 Total Patients

4.2. Inclusion Criteria:

In order to be eligible for study entry, subjects must comply with the following:

- Males or females from 3 months to 80 years old
- Signed written informed consent obtained prior to study entry
- Clinical diagnosis of WAS or XLT
- Platelet levels less than $75 \times 10^9/L$
- Adequate renal and hepatic function (creatinine and bilirubin less than or equal to $1.5 \times ULN$, AST and ALT less than or equal to $2.5 \times ULN$)

4.3. Exclusion Criteria:

Any patient is ineligible for study entry if he/she:

- Over the age of 80
- Pregnant or lactating women
- Fertile men who are not practicing or who are unwilling to practice birth control while enrolled in the study or until at least 6 months after treatment

- Aspirin, aspirin-containing compounds, salicylates, non-steroidal anti-inflammatory medications (NSAIDS), clopidogrel or ticlopidine, warfarin or other vitamin K antagonists, unfractionated or low molecular heparin within 7 days of first treatment
- Red blood cell transfusion in the past four weeks
- Elevated ($> 1.5 \times$ ULN) prothrombin time (PT) or partial thromboplastin time (PTT)
- New York Heart Classification III or IV heart disease. Other severe cardiovascular or cardiopulmonary disease, including COPD.
- Known HIV infection, hepatitis B or C infection
- Any infection requiring antibiotic treatment within 3 days
- Other concurrent medical or psychiatric conditions that, in the Investigator's opinion, may be likely to confound study interpretation or prevent completion of study procedures and follow-up examinations.
- Prior malignancy with less than a 5-year disease-free interval, excluding nonmelanoma skin cancers and carcinoma in situ of the cervix

Eligibility criteria for controls:

- a) Within 5 years of the age of the enrolled patient
- b) No overt hematologic diagnosis
- c) Male

4.4. Withdrawal Criteria:

1. Treatment with eltrombopag should be discontinued because of abnormal liver tests if any of the following 4 conditions apply:

- ALT levels ≥ 3 times upper limit of normal (ULN) and bilirubin levels > 1.5 times ($> 35\%$ conjugated bilirubin) ULN,
- (2) ALT levels ≥ 3 times ULN and appearance or worsening of hepatitis symptoms or rash,
- (3) ALT levels remain ≥ 3 times ULN for ≥ 4 weeks, or

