5.7. Treatment Plan

	Adults and children > 30 kg	Children < 30 kg	Frequency
Urinalysis	10 mL	5 mL	One Time (at screen)
Admission Panel (includes ALT, AST, bilirubin)	2 mL	2 mL	Every two weeks for the first month; monthly for year 1; every 2 months for year 3; every three months for years 3 - 6
CBC with Platelet and Differential and Immature Platelet Fraction (IPF)	2 mL	2 mL	Every two weeks for the first month; monthly for year 1; every 2 months for year 3; every three months for years 3 - 6
PT/PTT, D-Dimers, Fibrinogen	5 mL	2.5 mL	One time (at screen)
PFA	5 mL	2.5 mL	One time (at month 2)
Single Platelet Flow Cytometry	10 mL	2 mL	3 times (at screen, at month 1-3 and at year 1-2)

NOTE: see schedule of events on page 25

Control subject blood draw	30 mL	10-20 mL	One time
WAS Non-treatment subject blood draw	30mL	10-20mL	One time

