8.2. Study Design Considerations

Limited therapies exist to treat thrombocytopenia in WAS/XLT. IV gammaglobulin and corticosteroids, mainstays in ITP, are ineffective in WAS/XLT. Platelet transfusions only last for hours. The two treatments that affect the platelets in a more lasting manner are splenectomy and human stem cell transplantation (HSCT). Splenectomy successfully increases the platelet count in most patients but is associated with an increased risk of overwhelming post splenectomy sepsis (OPSS) due to the primary immune dysfunction seen in WAS/XLT. Human Stem Cell Transplantation (HSCT) is effective but has significant morbidity and mortality. Furthermore it is ideally postponed until after 24 months of age to allow TBI, which is too long to wait for affected infants with severe thrombocytopenia in view of the high risk of ICH. It is clearly necessary to establish improved therapy for thrombocytopenia in these children.

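### The 10-20 mL one-time draw that 5.7 lists for children under 30 kg is above the 3.1 age-based limit in any child under 1 year, counting age pro rata

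*Combined protocol and SAP*

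**What the plan says.** Section 3.1 adds two groups who give blood once and receive no study drug: ten control subjects and "ten additional WAS and XLT otherwise ineligible or unwilling patients who will not undergo study treatment". For the pediatric members of both groups it sets a limit by age for the single draw: "They will not be asked for more than 5-10 ml of blood per year of age up to a maximum of 30 ml total". It adds that their blood is being taken anyway for another purpose, and "therefore it will be a small amount of extra blood posing a minimal risk to the subject".

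The table in 5.7 gives the volume for this draw in two rows, "Control subject blood draw" and "WAS Non-treatment subject blood draw". Both rows show 30 mL for adults and children over 30 kg, and 10-20 mL for children under 30 kg. The split is by weight only. Neither row refers to age or to 3.1.

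On age, the inclusion criteria in 4.2 admit "Males or females from 3 months to 80 years old". A control must be male, free of overt hematologic disease and "Within 5 years of the age of the enrolled patient". Section 3.1 gives no lower age for the untreated patients.

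**The concern.** The two sections describe the same procedure in the same children and give volumes that cannot both be followed in an infant. The age limit falls toward zero as age falls; the table volume stops at 10 mL.

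These children get no study treatment, and 3.1 rests its statement of minimal risk on the extra volume being small. The age limit is what makes that statement concrete. A coordinator who takes the volume from the 5.7 table without going back to 3.1 could exceed it.

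The limit is also loosely worded. A ceiling given as a range has two values that differ twofold, and 3.1 does not say how to count age below 1 year. Someone who does apply 3.1 still cannot tell whether a 2-year-old may give 10 mL or 20 mL.

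**Working it through.** **Inputs.** Limit: 5 or 10 mL per year of age, ceiling 30 mL (3.1). Planned draw under 30 kg: 10 to 20 mL (5.7). Youngest age for study entry: 3 months (4.2), used here as an illustration for the one-time draw groups. Assumption: every child under 1 year weighs less than 30 kg.

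**Plan's own figure.** The 10-20 mL entry has no derivation, so there is nothing to reproduce. It equals the 3.1 limit at one age only, 2 years: 5 × 2 = 10 mL and 10 × 2 = 20 mL.

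**Formula.** Limit at a given age = the smaller of 30 mL and k × age in years, with k = 5 or 10 and age pro rata.

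| Age | Limit, k = 5 (mL) | Limit, k = 10 (mL) | 10 mL ÷ limit at k = 10 |
|---|---|---|---|
| 3 months (0.25 y) | 1.25 | 2.5 | 4 |
| 6 months (0.5 y) | 2.5 | 5 | 2 |
| 9 months (0.75 y) | 3.75 | 7.5 | 1.33 |
| 1 year | 5 | 10 | 1 |
| 2 years | 10 | 20 | 0.5 |
| 4 years | 20 | 30 (ceiling) | 0.33 |

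**Ages from which the table volume fits.**
- 10 mL: 10/10 = 1 year at k = 10; 10/5 = 2 years at k = 5.
- 20 mL: 20/10 = 2 years at k = 10; 20/5 = 4 years at k = 5.

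Below 1 year, 10 × age is less than 10, so no volume in the 5.7 range complies at either rate.

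**Other ways of counting age.** If a part year counts as a full year, an infant's limit is 5 or 10 mL. Exactly 10 mL then fits at k = 10, and nothing larger does. Completed years give 0 mL under age 1, which would bar any draw and is not a sensible reading.

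**Can infants be in these groups?** Yes. The untreated group has no stated lower age. A control under 1 year satisfies the 5-year rule for any enrolled patient under 1 + 5 = 6 years who is within 5 years of him. Section 8.2 mentions infants with the disease ("too long to wait for affected infants with severe thrombocytopenia in view of the high risk of ICH"), but that sentence concerns the timing of transplantation and does not say who will give a one-time draw.

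**The case against.** The strongest reply is that a ceiling and a nominal volume can coexist. Section 3.1 is worded as a prohibition, the table claims no priority over it, and the natural reading is that the ceiling binds and the table applies where it fits. From age 2, 10 mL meets the limit at either rate, and because 5.7 gives a range, staff can choose the lower end. Infants may be few or none: the two groups total 20 people, the pediatric members must already be having a draw unrelated to acute illness, and a 3-month-old patient could be matched to a 4-year-old control, for whom 20 mL fits at either rate.

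Most of this stands. It limits how often the conflict can arise, and it means the table could, rather than would, lead to an excess draw. It does not remove the conflict. Under 1 year, with age pro rata, the lowest volume in 5.7 cannot comply, and reading 3.1 as controlling still leaves open whether 5 or 10 mL per year applies.

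A reader might infer more: that infants are planned for these groups, or that 10-20 mL is unsafe for them. The documents support neither. No number of infants is given. The ratios measure distance from the plan's own age rule; the documents give no limit per kg or by blood volume against which to judge harm. Section 5.1 itself plans about 10-20 mL at screening for treated subjects, who may be as young as 3 months.

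**Conclusion.** The inconsistency is real and narrow. With age pro rata, the 10 mL minimum in 5.7 is above the 3.1 limit in any child under 1 year even at 10 mL per year: 4 times the limit at 3 months and 2 times at 6 months. The 20 mL end is above the limit below age 2 at 10 mL per year and below age 4 at 5 mL per year. No other section reconciles the two.

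The result for infants rests on counting age pro rata; the single exception is a part year counted as a whole one, at the higher rate and at exactly 10 mL. The practical reach depends on how many young children give a one-time draw, which the plan does not state. Sample size, the primary endpoint and every planned analysis are unaffected. It deserves correction because it concerns a protective limit for untreated children and takes a few words to settle.

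**What to change.** In 3.1, replace the range with a single maximum. One option is 10 mL per year of age, the most the current text allows, pro rata by month under 1 year, and at most 30 mL in one draw. The IRB may prefer a lower rate.

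In 5.7, change the under-30 kg entry in both one-time draw rows to 'up to 20 mL, not to exceed the 3.1 limit'. The 10 mL floor has to go; adding a cross-reference to 10-20 mL would leave a minimum above the maximum in infants. At 10 mL per year the permitted draw becomes 2.5 mL at 3 months, 5 mL at 6 months, 10 mL at 1 year and 20 mL from 2 years.

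The cost is one sentence and two table cells, plus some lost assays in the youngest children. The under-30 kg volumes in 5.7 for the blood count with immature platelet fraction (2 mL), PFA (2.5 mL) and flow cytometry (2 mL) total 6.5 mL, which at 10 mL per year fits only from 6.5/10 = 0.65 years, about 8 months. The stem-cell work of specific aim 1 has no stated volume and would come on top. Stating which assay takes priority when blood is short would help but is optional.

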Eltrombopag starting doses for children < 50kg will be scaled by body weight and the starting dose will be approximately 2 mg/kg once daily unless they are of East Asian origin in which case they will use approximately 1 mg/kg as their initial dose. This starting dose is based on the findings of GlaxoSmithKline's PETIT2 study: Eltrombopag for children with chronic immune thrombocytopenia (PETIT2): a randomised, multicentre, placebo-controlled trial.

This dosing schedule is based on those used in GlaxoSmithKline's 'PETIT' study: Eltrombopag in Pediatric patients with Thrombocytopenia from ITP.

For young children unable to swallow a tablet, eltrombopag powder for oral suspension (Eltrombopag PfOS) will be used. Each sachet contains eltrombopag equivalent to 20mg per gm of powder. Please see Appendix 3 for details and dose adjustment guidelines for subjects receiving the suspension formulation. Repeat assessment with the same testing will be performed at week 4. Dose adjustment will be based on the monthly monitoring of the platelet count.

The IPF will be measured at each visit with the CBC. Platelet count data will be collected throughout the study and used as part of the assessment of efficacy. Platelet count data will be collected as part of the CBC monthly during the first year of administration of study drug and at any dose change (eltrombopag or concomitant medication). If a subject continues on a stable dose during any stage of the study for greater than 4 weeks, a CBC (including platelet count) with differential will be performed no less frequently than every 4 weeks. Further information regarding reduction in use of concomitant medications for thrombocytopenia, use of rescue therapy, incidence and severity of bleeding and other symptoms associated with thrombocytopenia and infections will also be collected and summarized.

Platelet function will be assessed by whole blood flow cytometry as described by and in collaboration with [name] (see appendix for attached abstracts).

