4.4.2. Patient Stopping Rules

1. Malignancy
2. Transaminase and bilirubin rules
3. Worsening cataracts
4. No increase in the platelet count despite dose increases to > 1.5 mg/kg body weight

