10. APPENDICES

1. SCHEDULE OF EVENTS ON THE LAST PAGE OF THE PROTOCOL (PAGE 25).

2. WEEKLY DOSE ADJUSTMENT FOR PLATELET COUNTS:

PLATELET COUNT	DOSE ADJUSTMENT
>200 Gi/L	dose reduced by at least 5%
50 to 200 Gi/L	Maintain current dose
<50 Gi/L and/or Significant Bleeding	Increase daily dose by at least 5% up to 75mg daily

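### The 2 mg/kg paediatric start has no mg maximum, so above about 37.5 kg it exceeds the 75 mg that limits increases; the 1.5 mg/kg non-response stop does not fit these doses either

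*Combined protocol and SAP*

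**What the plan says.** Section 3.1 sets the paediatric start: "Eltrombopag starting doses for children < 50kg will be scaled by body weight and the starting dose will be approximately 2 mg/kg once daily". The sentence goes on to give about 1 mg/kg for East Asian children. Section 5.1 repeats the 2 mg/kg start, again with no maximum in mg, and leaves out that exception. Another sentence in 3.1 puts treatment patients in general on 2 mg/kg with no weight limit. For heavier patients, 3.1 says "patients over 50 kg will start at 50 mg daily unless they are of East Asian origin", in which case the start is 25 mg.

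The figure of 75 mg appears in two places. Section 3.1 says "doses between 12.5mg every other day and 75mg once daily are anticipated to be required" to keep counts in range. The adjustment table in Appendix item 2 says, for a count below 50 Gi/L or significant bleeding, "Increase daily dose by at least 5% up to 75mg daily". In the same table a count of 50 to 200 Gi/L means "Maintain current dose", and above 200 Gi/L the instruction is "dose reduced by at least 5" per cent. Suspension Table 1 stops at 25 kg and 50 mg. On tablet strengths, 3.1 says "it is also available for clinical studies in 12.5 mg tablets", but no rounding rule is given.

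Section 4.4.2, rule 4, stops a patient for "No increase in the platelet count despite dose increases to > 1.5 mg/kg body weight". Section 8.3.1.1 counts a platelet count above 50,000/ul at any time in the first 12 weeks as a response.

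**The concern.** A day-1 dose should not be higher than titration is allowed to reach. Here a child of 38 to 49 kg can be started above 75 mg by direct multiplication, while a slightly heavier patient starts at about half that dose. Once such a dose is given, the adjustment table offers no route back to 75 mg unless the count goes above 200 Gi/L. Section 6.3 gives the safety bearing: excessive doses may drive platelet counts to a level that produces thrombosis.

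The second strand is the individual non-response stop. Its threshold of 1.5 mg/kg does not match a 2 mg/kg start at one end or a 75 mg limit at the other. At stake there is futility, not toxicity: who is taken off an ineffective drug, and when, on a schedule that runs to month 72.

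**Working it through.** **Reproducing the plan's own table.** In suspension Table 1 the initial dose is 2 × weight, and the step is 30% of that, rounded up. At 8 kg: 2 × 8 = 16 mg, 0.30 × 16 = 4.8, step 5 mg. At 25 kg: 2 × 25 = 50 mg, 0.30 × 50 = 15 mg. All 18 rows reproduce in both columns. Above 25 kg staff must calculate the dose themselves.

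**Where the start passes 75 mg.** 75 / 2 = 37.5 kg.

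| Weight | Start at 2 mg/kg | Relative to 75 mg | 75 mg as mg/kg |
|---|---|---|---|
| 38 kg | 76 mg | 1.01 | 1.97 |
| 45 kg | 90 mg | 1.20 | 1.67 |
| 49 kg | 98 mg | 1.31 | 1.53 |

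Just over 50 kg the start is 50 mg, so the step at 50 kg is 98 / 50 = 1.96-fold.

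**Does tablet rounding remove it?** Assume 12.5 mg steps, since no rule is given. Rounding to the nearest step exceeds 75 mg from 81.25 / 2 = 40.6 kg. Rounding down exceeds it from 87.5 / 2 = 43.75 kg. The band narrows but does not disappear.

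**What Appendix item 2 does with a 98 mg dose.** At 50 to 200 Gi/L it is kept. Below 50 Gi/L an increase that ends at 75 mg cannot be carried out from 98 mg. Only above 200 Gi/L is it lowered.

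**How soon a high count would be seen.** Section 6.1 promises weekly CBCs during dose adjustment, but the schedule of events shows week 2, week 4, then monthly. On that schedule the first count after dosing is at week 2.

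**How many children.** About 80% of 15 is 12. Their weights are not given, so the number in the band is anywhere from 0 to 12.

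**Stopping rule 4, by group.**
- *2 mg/kg starters below 37.5 kg.* They are above 1.5 mg/kg before any increase, so the threshold adds nothing. The first increase takes them to 2 × 1.05 = 2.1 mg/kg (5% step) or, at 10 kg on Table 1, 26 / 10 = 2.6 mg/kg. It could come at week 2 under the two-weekly limit in 8.3.1.1, or about week 4 if the monthly adjustment in 3.1 is followed. That is 12 − 2 = 10 or 12 − 4 = 8 weeks before the response window closes.
- *2 mg/kg starters from 37.5 to 50 kg.* No increase is permitted, so the condition that doses were increased cannot be met.
- *50 kg or more.* The most that 75 mg allows is 75 / 50 = 1.50 mg/kg, 75 / 60 = 1.25 and 75 / 70 = 1.07. A dose above 1.5 mg/kg cannot be reached.
- *East Asian children under 50 kg, starting at 1 mg/kg.* Here the threshold does work. Two 30% steps give 1.3 × 1.3 = 1.69 mg/kg. One step is enough only if the mg steps of Table 1, built for a 2 mg/kg start, are used: at 10 kg, (10 + 6) / 10 = 1.60 mg/kg.

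**The case against.** A reader might infer that the protocol breaks its own maximum dose and exposes children to a demonstrated hazard, so that dosing should wait for an amendment. The documents do not support that. The 75 mg figure is an anticipated range and a limit on increases; nowhere is it stated as a cap on the start. The 2 mg/kg is approximate, and 3.1 rests it on a randomised paediatric trial whose dosing limits cannot be seen from here. Section 6.3 says that thrombosis can occur at any count, but it links excessive dose to thrombosis through excessive counts, and a child kept on dose at 50 to 200 Gi/L has no such count. Above 200 Gi/L the dose is reduced, and the liver and thrombosis stops apply throughout. No affected child is shown to exist.

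One can also argue that 3.1 and Appendix item 2, read together, imply a 75 mg study ceiling that was simply not repeated, and that treatment is started at a single centre that would know this. That makes a 98 mg start less likely. It does not settle the matter, because the operative sentences in 3.1 and 5.1 do not say so, and the table that might have shown a ceiling ends at 25 kg.

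On rule 4, a reader might infer that non-responders have no futility protection at all. That goes too far: the study-level stop in 4.4.1 (no rise above 30,000 in 8 consecutive patients) still applies, as do the individual safety stops. The early-stop risk for lighter children is also narrow, since any rise in the count avoids it.

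These points lower the severity. They do not remove the inconsistency.

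**Conclusion.** The point holds as an inconsistency between operative dosing rules with a safety bearing. It should be fixed, but it is not a must-fix. As written, non-East Asian children between about 37.5 and 50 kg have a calculated start above 75 mg, by 1% at 38 kg and 31% at 49 kg. On the assumed 12.5 mg steps the lower edge moves to 40.6 kg (nearest) or 43.75 kg (down). The finding rests on taking 2 mg/kg at face value and on there being no start cap elsewhere in the documents; none was found. No sample-size or analysis figure changes.

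The rule 4 mismatch is secondary. Patients of 50 kg or more who do not respond have no working individual non-response stop, and for 2 mg/kg starters the threshold is passed on day 1. The East Asian exception missing from 5.1 and Table 1 is editorial.

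**What to change.** (i) In 3.1 and 5.1, give the start for children under 50 kg as about 2 mg/kg per day, or about 1 mg/kg if of East Asian origin, with a maximum of 75 mg per day. Restrict the general 2 mg/kg sentence in 3.1 to children under 50 kg with the same maximum; otherwise an uncapped instruction remains. This uses the sponsor's own figure. The cost is a lower start in the band: at 49 kg, 1 − 75/98 = 23%, or 2.0 down to 1.53 mg/kg. A step from 75 to 50 mg remains at 50 kg, and the sponsor should confirm that it is intended. If starts above 75 mg are intended, the text should say so, and 3.1 and Appendix item 2 should be amended to match.

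(ii) In 4.4.2, replace rule 4 with no platelet increase at the highest permitted (75 mg) or tolerated dose, not applied before the 12-week response window ends. This is needed even with (i), because children of 37.5 to 50 kg would then start at the maximum. The cost is that some non-responders stay on drug longer.

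(iii) Editorial: carry the East Asian child exception into 5.1 and Table 1.

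All three are wording changes, with no added patients, visits or procedures. The sponsor should also bring the CBC frequency in 6.1 and the schedule of events into line.
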